# 3.5 **Prior and Concomitant Medications**

### Table 14.1.4.1 Summary of Prior Medications (Intent-To-Treat Population)

Therapeutic Subgroup Chemical Subgroup Grouped Preferred Term [a]	Plitidepsin 2.5mg (N=XXX) n (%)	Plitidepsin 1.5mg (N=XXX) n (%)	Control Arm (N=XXX) n (%)	Total (N=XXX) n (%)
Number of Patients with any Prior Medication	xxx (xxx.x)	xxx (xxx.x)	xxx (xxx.x)	xxx (xxx.x)
WHO ATC Level 2	xxx (xxx.x)	xxx (xxx.x)	xxx (xxx.x)	xxx (xxx.x)
WHO ATC Level 4	xxx (xxx.x)	xxx (xxx.x)	xxx (xxx.x)	xxx (xxx.x)
Grouped Preferred Term 1	xxx (xxx.x)	xxx (xxx.x)	xxx (xxx.x)	xxx (xxx.x)
Grouped Preferred Term 2	xxx (xxx.x)	xxx (xxx.x)	xxx (xxx.x)	xxx (xxx.x)
WHO ATC Level 2	xxx (xxx.x)	xxx (xxx.x)	xxx (xxx.x)	xxx (xxx.x)
WHO ATC Level 4	xxx (xxx.x)	xxx (xxx.x)	xxx (xxx.x)	xxx (xxx.x)
Grouped Preferred Term 1	xxx (xxx.x)	xxx (xxx.x)	xxx (xxx.x)	xxx (xxx.x)
Grouped Preferred Term 2	xxx (xxx.x)	xxx (xxx.x)	xxx (xxx.x)	xxx (xxx.x)
etc.				

N = number of patients in analysis set; n = number of patients with data available; % = percentages are calculated based on N as the denominator.

ATC = Anatomical Therapeutic Chemical, WHO = World Health Organization.

Notes: Prior medications are those taken prior to screening with a stop date prior to the first dose date of any study drug administration.

Prior medications were coded using WHODrug Global, &whodrug.

[a] Within a Chemical Subgroup, a patient may have reported more than one grouped preferred term. Patients are counted once for each grouped preferred term and each Chemical Subgroup. Reference: Listing 16.2.4.4

- Table template TCM001.
- Sort by descending order of Anatomical Group, then descending order of Chemical Subgroup, then descending order of grouped preferred term in the total column. Where groups or terms tie these should be sorted alphabetically.
- Assign the version of WHO Drug Dictionary to &whodrug. macro variable as Format Bx, Version Month YYYY and update the version of WHO Drug Dictionary used for coding as needed.
- For coded medications with missing WHO ATC Level 4, present the WHO ATC Level 3 in place of the WHO ATC Level 4. If WHO ATC Level 3 is also missing, present WHO ATC Level 2 in place of the WHO ATC Level 4.

# Table 14.1.4.2 Summary of Concomitant Medications, excluding COVID-19 Antiviral Therapies or Immunomodulatory Concomitant Medications (Intent-To-Treat Population)

Therapeutic Subgroup Chemical Subgroup Grouped Preferred Term [a]	Plitidepsin 2.5mg (N=XXX) n (%)	Plitidepsin 1.5mg (N=XXX) n (%)	Control Arm (N=XXX) n (%)	Total (N=XXX) n (%)
Number of Patients with any Concomitant Medication	xxx (xxx.x)	xxx (xxx.x)	xxx (xxx.x)	xxx (xxx.x)
WHO ATC Level 2	xxx (xxx.x)	xxx (xxx.x)	xxx (xxx.x)	xxx (xxx.x)
WHO ATC Level 4	xxx (xxx.x)	xxx (xxx.x)	xxx (xxx.x)	xxx (xxx.x)
Grouped Preferred Term 1	xxx (xxx.x)	xxx (xxx.x)	xxx (xxx.x)	xxx (xxx.x)
Grouped Preferred Term 2	xxx (xxx.x)	xxx (xxx.x)	xxx (xxx.x)	xxx (xxx.x)
WHO ATC Level 2	xxx (xxx.x)	xxx (xxx.x)	xxx (xxx.x)	xxx (xxx.x)
WHO ATC Level 4	xxx (xxx.x)	xxx (xxx.x)	xxx (xxx.x)	xxx (xxx.x)
Grouped Preferred Term 1	xxx (xxx.x)	xxx (xxx.x)	xxx (xxx.x)	xxx (xxx.x)
Grouped Preferred Term 2	xxx (xxx.x)	xxx (xxx.x)	XXX (XXX.X)	xxx (xxx.x)
etc.				

N = number of patients in analysis set; n = number of patients with data available; % = percentages are calculated based on N as the denominator.

ATC = Anatomical Therapeutic Chemical, WHO = World Health Organization.

Notes: Concomitant medications are those with a start date on or after the first dose date of any study drug administration, or those with a start date before the first dose date of any study drug administration and a stop date on or after the first dose date of any study drug administration or ongoing at the end of the study.

COVID-19 antiviral therapies or immunomodulatory concomitant medications are excluded from this table.

Concomitant medications were coded using WHODrug Global, &whodrug.

[a] Within a Chemical Subgroup, a patient may have reported more than one grouped preferred term. Patients are counted once for each grouped preferred term and each Chemical Subgroup. Reference: Listing 16.2.4.5

Programming notes (not part of the table):

- *Table template TCM002.*
- Sort by descending order of Anatomical Group, then descending order of Chemical Subgroup, then descending order of grouped preferred term in the total column. Where groups or terms tie these should be sorted alphabetically.

Assign the version of WHO Drug Dictionary to &whodrug. macro variable as Format Bx, Version Month YYYY and update the version of WHO Drug Dictionary used for coding as needed.

• For coded medications with missing WHO ATC Level 4, present the WHO ATC Level 3 in place of the WHO ATC Level 4. If WHO ATC Level 3 is also missing, present WHO ATC Level 2 in place of the WHO ATC Level 4.

Therapeutic Subgroup Chemical Subgroup Grouped Preferred Term [a]	Plitidepsin 2.5mg (N=XXX) n (%)	Plitidepsin 1.5mg (N=XXX) n (%)	Control Arm (N=XXX) n (%)	Total (N=XXX) n (%)
Number of Patients with any COVID-19 Antiviral Therapies or Immunomodulatory Concomitant Medication	xxx (xxx.x)	xxx (xxx.x)	xxx (xxx.x)	xxx (xxx.x)
WHO ATC Level 2	xxx (xxx.x)	xxx (xxx.x)	xxx (xxx.x)	xxx (xxx.x)
WHO ATC Level 4	xxx (xxx.x)	xxx (xxx.x)	xxx (xxx.x)	xxx (xxx.x)
Grouped Preferred Term 1	xxx (xxx.x)	xxx (xxx.x)	xxx (xxx.x)	xxx (xxx.x)
Grouped Preferred Term 2	xxx (xxx.x)	xxx (xxx.x)	xxx (xxx.x)	xxx (xxx.x)
WHO ATC Level 2	xxx (xxx.x)	xxx (xxx.x)	xxx (xxx.x)	xxx (xxx.x)
WHO ATC Level 4	xxx (xxx.x)	xxx (xxx.x)	xxx (xxx.x)	xxx (xxx.x)
Grouped Preferred Term 1	xxx (xxx.x)	xxx (xxx.x)	xxx (xxx.x)	xxx (xxx.x)
Grouped Preferred Term 2	xxx (xxx.x)	xxx (xxx.x)	xxx (xxx.x)	xxx (xxx.x)
etc.				

#### Table 14.1.4.3 Summary of COVID-19 Antiviral Therapies or Immunomodulatory Concomitant Medications (Intent-To-Treat Population)

N = number of patients in analysis set; n = number of patients with data available; % = percentages are calculated based on N as the denominator.

ATC = Anatomical Therapeutic Chemical, WHO = World Health Organization.

Notes: Concomitant medications are those with a start date on or after the first dose date of any study drug administration, or those with a start date before the first dose date of any study drug administration and a stop date on or after the first dose date of any study drug administration or ongoing at the end of the study.

Only COVID-19 antiviral therapies or immunomodulatory concomitant medications are presented in this table.

Concomitant medications were coded using WHODrug Global, &whodrug.

[a] Within a Chemical Subgroup, a patient may have reported more than one grouped preferred term. Patients are counted once for each grouped preferred term and each Chemical Subgroup. Reference: Listing 16.2.4.7

Programming notes (not part of the table):

- Table template TCM002.
- Sort by descending order of Anatomical Group, then descending order of Chemical Subgroup, then descending order of grouped preferred term in the total column. Where groups or terms tie these should be sorted alphabetically.

• Assign the version of WHO Drug Dictionary to &whodrug. macro variable as Format Bx, Version Month YYYY and update the version of WHO Drug Dictionary used for coding as needed.

• For coded medications with missing WHO ATC Level 4, present the WHO ATC Level 3 in place of the WHO ATC Level 4. If WHO ATC Level 3 is also missing, present WHO ATC Level 2 in place of the WHO ATC Level 4.

# **3.6** Signs and Symptoms

Characteristic Statistic	Plitidepsin 2.5mg (N=XXX)	Plitidepsin 1.5mg (N=XXX)	Control Arm (N=XXX)	Total (N=XXX)
Time between Onset Date of COVID-19 Symptoms and Initiation of Study Treatment (days) [a]				
n	XXX	XXX	XXX	XXX
Mean (SD)	xx.x (xx.xx)	xx.x (xx.xx)	xx.x (xx.xx)	xx.x (xx.xx)
Median	XX.X	XX.X	XX.X	XX.X
Q1, Q3	XX.X, XX.X	xx.x, xx.x	xx.x, xx.x	XX.X, XX.X
Min, Max	XX, XX	XX, XX	XX, XX	XX, XX
History of Fever, n (%)				
Yes	xxx (xxx.x)	xxx (xxx.x)	xxx (xxx.x)	xxx (xxx.x)
No	xxx (xxx.x)	xxx (xxx.x)	xxx (xxx.x)	xxx (xxx.x)
Unknown	xxx (xxx.x)	xxx (xxx.x)	xxx (xxx.x)	xxx (xxx.x)
Cough, n (%)				
Yes, non-productive	xxx (xxx.x)	xxx (xxx.x)	xxx (xxx.x)	xxx (xxx.x)
Yes, productive	xxx (xxx.x)	xxx (xxx.x)	xxx (xxx.x)	xxx (xxx.x)
Yes, with haemoptysis	xxx (xxx.x)	xxx (xxx.x)	xxx (xxx.x)	xxx (xxx.x)
No	xxx (xxx.x)	xxx (xxx.x)	xxx (xxx.x)	xxx (xxx.x)
Unknown	xxx (xxx.x)	xxx (xxx.x)	xxx (xxx.x)	xxx (xxx.x)

### Table 14.1.5.1 Summary of Signs and Symptoms (Intent-To-Treat Population)

<continue for the following signs and symptoms with the subcategories [Yes/No/Unknown]: sore throat, runny nose (rhinorrhoea), wheezing, shortness of breath, lower chest wall indrawing, chest pain, conjunctivitis, lymphadenopathy, headache, loss of smell (anosmia), loss of taste (ageusia), seizures, fatigue/malaise, anorexia, altered consciousness/confusion, muscle aches (myalgia), joint pain (arthralgia), inability to walk, abdominal pain, diarrhoea, vomiting/nausea, skin rash, bleeding (haemorrhage), and other symptom(s).>

N = number of patients in analysis set; n = number of patients with data available; % = percentages are calculated based on N as the denominator.

SD = Standard deviation; Q1 =25th percentile; Q3 = 75th percentile; Min = Minimum; Max = Maximum.

[a] Time between onset date of COVID-19 symptoms and initiation of study treatment (days) = (date of the first study drug administration - onset date of COVID-19 symptoms) Reference: Listing 16.2.4.9

- Table template TDM002.
- A "Missing" category should only be presented under the subcategories for any Sign and Symptom in case of missing data.

# 3.7 Primary Efficacy Endpoint

#### Table 14.2.1.1.1 Time to Sustained Withdrawal of Oxygen Supplementation (Intent-To-Treat Population)

Variable	Plitidepsin 2.5mg (N=XXX)	Plitidepsin 1.5mg (N=XXX)	Control Arm (N=XXX)	
Patients who Reported Sustained Withdrawal of Oxygen				
Supplementation, n (%) Censored Patients, n (%)	xxx (xx.x) xxx (xx.x)	xxx (xx.x) xxx (xx.x)	xxx (xx.x) xxx (xx.x)	
Time-to Sustained Withdrawal of Oxygen Supplementation (days) 95%				
25th percentile	xx.x (xx.x, xx.x)	xx.x (xx.x, xx.x)	xx.x (xx.x, xx.x)	
Median	xx.x (xx.x, xx.x)	xx.x (xx.x, xx.x)	xx.x (xx.x, xx.x)	
75th percentile	xx.x (xx.x, xx.x)	xx.x (xx.x, xx.x)	xx.x (xx.x, xx.x)	
Mean (SE)	xx.x (xx.x)	xx.x (xx.x)	xx.x (xx.x)	
Stratified Log-Rank Test				
2-sided p-value [b]	X.XXX	X.XXX		
2-sided p-value adjusted for Multiplicity [b,c]	X.XXX	X.XXX		
Supportive Analysis - Stratified Cox Regression Model				
Hazard Ratio [d,e]	X.XXX	X.XXX		
95% CI for Hazard Ratio [d,e]	X.XXX - X.XXX	X.XXX - X.XXX		
2-sided p-value [d]	X.XXX	X.XXX		

N = number of patients in analysis set. % = percentages are calculated based on N as the denominator.

CI = Confidence interval; SE = Standard Error.

Notes: Sustained withdrawal of oxygen supplementation (in days) with no subsequent reutilisation during remaining study period is defined as the first day, from randomisation through completion of the study, on which a patient

i. satisfies categories 0 to 4 on the 11-point WHO Clinical Progression Scale, and

ii. has no subsequent reutilisation of oxygen supplementation (5 to 10 on the 11-point WHO Clinical Progression Scale)

[a] Calculated using the Kaplan-Meier estimator. CIs derived based on Brookmeyer-Crowley method and using a log log transformation.

[b] 2-sided p-values calculated using a stratified log-rank test, including the fixed effect of the treatment group and levels of the randomisation stratification factors, ie, geographical region (Europe vs. Rest of the World), Charlson Comorbidity Index (0-1 vs. >1) and pre-baseline Barthel index ( $\geq$ 90 versus <90) as derived using the eCRF data as covariates.

[c] Stratified log-rank test p-values adjusted for multiplicity using the Hochberg step-up procedure.

[d] Hazard Ratio, 95% CI and 2-sided p-values calculated using a stratified Cox proportional-hazards regression model, including the fixed effect of the treatment group and levels of the randomisation stratification factors, ie, geographical region (Europe vs. Rest of the World), Charlson Comorbidity Index (0-1 vs. >1) and pre-baseline Barthel index ( $\geq$ 90 versus <90) as derived using the eCRF data as covariates. Hazard Ratio > 1 favours a Plitidepsin arm to be associated with a shorter time to sustained withdrawal of oxygen supplementation than Control Arm.

[e] Statistics calculated relative to Control Arm.

Reference: Listing 16.2.6.5

Programming notes (not part of the table):

• Table template TEF011A.

- The displayed xxx do not reflect actual decimal precision. Please follow Section 2.11 for rounding rules.
- If 25th percentile, median or 75th percentile is not reached, present as "NR".

 Table 14.2.1.1.2 Time to Sustained Withdrawal of Oxygen Supplementation - Proportional Hazard Assumption and Restricted Mean Survival (Intent-To-Treat Population)

Variable	Time Dependent	Plitidepsin 2.5mg	Plitidepsin 1.5mg	Control Arm
	Covariate	(N=XXX)	(N=XXX)	(N=XXX)
p-value [a]	x.xxxx			
Restricted Mean Survival at Day 4		X.XXX	X.XXX	X.XXX
Restricted Mean Survival at Day 8		X.XXX	X.XXX	X.XXX
Restricted Mean Survival at Day 15		X.XXX	X.XXX	X.XXX
Restricted Mean Survival at Day 31		X.XXX	X.XXX	X.XXX

N = number of patients in analysis set.

Notes: Sustained withdrawal of oxygen supplementation (in days) with no subsequent reutilisation during remaining study period is defined as the first day, from randomisation through completion of the study, on which a patient

i. satisfies categories 0 to 4 on the 11-point WHO Clinical Progression Scale, and

ii. has no subsequent reutilisation of oxygen supplementation (5 to 10 on the 11-point WHO Clinical Progression Scale)

[a] Time dependent covariate p-value calculated using a stratified Cox proportional-hazards regression model, including the fixed effect of the treatment group and its time dependent covariate, i.e., treatment group\*log(time). Censored patients at time 0 will not be used in the model.

Reference: Listing 16.2.6.5

Programming notes (not part of the table):

• Table template TEF011A.

• The displayed xxx do not reflect actual decimal precision. Please follow Section 2.11 for rounding rules.

• If time dependent covariate p-value is <0.05 then restricted mean survival at Day 4, Day 8, Day 15 and Day 31 will be calculated. Otherwise, restricted mean survival at Day 4, Day 8, Day 15 and Day 31 will not be calculated and their rows will be removed from the table.

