## 2.2 Overall Study Design

This is a randomised, multicentre, open-label, controlled Phase 3 study in which adults requiring hospital admission and oxygen supplementation for management of moderate COVID-19 infection will be randomised in 1:1:1 to:

- Plitidepsin 1.5 mg arm: Patients will receive plitidepsin 1.5 mg/day intravenous (IV) in addition to dexamethasone on days 1 to 3;
- Plitidepsin 2.5 mg arm: Patients will receive plitidepsin 2.5 mg/day IV in addition to dexamethasone on days 1 to 3;
- Control arm: Patients will receive dexamethasone IV on Days 1 to 3. Additionally, in accordance with local treatment guidelines, patients in this group may receive a regulatory-approved antiviral treatment.

The study allows up to a total cumulative dose of 60 mg of dexamethasone base (calculation of the total dose will also include corticosteroids administered within 72 hours before the start of the study treatment and dexamethasone administered as premedication).

Randomisation will be stratified for 3 factors:

- Geographical region (Europe vs. Rest of the World);
- Charlson Comorbidity Index (0-1 vs. >1); and
- Barthel Index (≥90 versus <90)

From treatment initiation on Day 1, patients will be followed in the hospital for at least 4 days and then through Day 31 ( $\pm$ 3 days) or resolution/stabilisation of treatment-related adverse events (AEs), treatment-emergent adverse events (TEAEs) of special interest, and serious adverse events (SAEs). Patients discharged from the hospital prior to Day 8 will return to an out-patient clinic for assessments on Days 8 ( $\pm$ 1 day), and 31 ( $\pm$ 3 days). On Day 15 ( $\pm$ 1 day), patients will be followed up in remote or on-site visit (Appendix 4).

An independent Data Monitoring Committee (IDMC) will oversee study conduct (safety and primary endpoint), including analysis of summary safety data as per the trial requirements.

The study is expected to randomise approximately 609 patients (203 in each arm) over a period of 20 months.

Patients will be considered to be on study from the signature of the informed consent form until the end of the follow-up period, that is, completion of the protocol-specified follow-up visit on Day 31 ( $\pm$ 3 days) or until resolution/ stabilisation of treatment-related AEs, TEAEs of special interest, and SAEs that occurred through Day 31, whichever is longer.

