#### 7.6.1 Primary Efficacy Analysis

Time to sustained withdrawal of oxygen supplementation (in days) with no subsequent reutilisation during remaining study period is defined as the first day, from randomisation through completion of the study, on which a patient

- i. satisfies categories 0 to 4 on the 11-point WHO Clinical Progression Scale, and
- ii. has no subsequent reutilisation of oxygen supplementation (5 to 10 on the 11-point WHO Clinical Progression Scale)

Patients who reported sustained withdrawal of oxygen supplementation will be considered as an event on the date when patient meets categories 0 to 4 on the 11-point WHO Clinical Progression Scale and has no subsequent reutilisation of oxygen supplementation. Otherwise, in case of early study discontinuation due to any reason the patient will be censored at the date of the early study discontinuation. Otherwise, the patient will be censored at the date of the Day 31 visit or death date, whichever is first. If the patient was lost to follow-up between day 15 and day 31 visit, and there is an attempt of contact and study discontinuation on or after the day 31 visit due date, the patient will be censored at day 31.

Time-to sustained withdrawal of oxygen supplementation (days) = (date of event or censoring – date of randomisation)

If date of event is the same as the randomisation date then time-to sustained withdrawal of oxygen supplementation will be considered as 1 day. If no data is available then time will be censored at time 0.

Time-to sustained withdrawal of oxygen supplementation will be analysed using the Kaplan-Meier method and 25th percentile, median and 75th percentile time will be presented by treatment group together with 95% CIs. The 95% CIs will be computed based on Brookmeyer-Crowley method and using a log log transformation. The mean time to sustained withdrawal of oxygen supplementation and its standard error will be also presented by treatment group.

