#### 7.6.2.1 Key Secondary Efficacy Endpoint

Time to sustained (ie, with no subsequent readmission to Day 31) hospital discharge (in days), defined as the first day, from randomisation through completion of the study, on which a patient

- i. discharges from the hospital, and
- ii. has no subsequent re-admission
Patients who reported sustained hospital discharge will be considered as an event on the date of discharge. Otherwise, in case of early study discontinuation due to any reason the patient will be censored at the date of the early study discontinuation. Otherwise, the patient will be censored at the date of the Day 31 visit or death date, whichever is first.

Time-to sustained hospital discharge (days) = (date of event or censoring – date of randomisation)

If date of event is the same as the randomisation date then time-to sustained hospital discharge will be considered as 1 day. If no data is available then time will be censored at time 0.

Time-to sustained hospital discharge will be analysed using the Kaplan-Meier method and 25th percentile, median and 75th percentile time will be presented by treatment group together with 95% CIs. The 95% CIs will be computed based on Brookmeyer-Crowley method and using a log log transformation. The mean time to hospital discharge and its standard error will be also presented by treatment group.

Time-to sustained hospital discharge between each dose of plitidepsin versus control arm will be compared using a stratified log-rank test, including the randomisation stratification factors as covariates, ie, Geographical Region (Europe vs. Rest of the World), Charlson Comorbidity index (0-1 vs. >1) and pre-baseline Barthel index ( $\geq$ 90 versus <90) as derived using the eCRF data. The 2-sided p-values for the comparison of each dose of plitidepsin versus control arm will be presented.

In the event that the primary efficacy endpoint of time to sustained withdrawal of oxygen supplementation is significant for both doses in the ITT population, the 2-sided p-values from the stratified log-rank test for the key secondary efficacy endpoint will be adjusted for multiplicity using the Hochberg step-up procedure to preserve the type 1 error rate in the comparison of each dose of plitidepsin versus control arm. This adjustment will not apply if the accrual in any of the experimental arms is stopped after the interim analysis.

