# 3.8 Key Secondary Efficacy Endpoints

#### Table 14.2.2.1.1 Time to Sustained Hospital Discharge (Intent-To-Treat Population)

Plitidepsin 2.5mg (N=XXX)	Plitidepsin 1.5mg (N=XXX)	Control Arm (N=XXX)
	····· (··· ·· ·)	
XXX (XX.X)	XXX (XX.X)	XXX (XX.X)
xx.x (xx.x, xx.x)	xx.x (xx.x, xx.x)	xx.x (xx.x, xx.x)
xx.x (xx.x, xx.x)	xx.x (xx.x, xx.x)	xx.x (xx.x, xx.x)
xx.x (xx.x, xx.x)	xx.x (xx.x, xx.x)	xx.x (xx.x, xx.x)
xx.x (xx.x)	xx.x (xx.x)	xx.x (xx.x)
X.XXX	X.XXX	
X.XXX	X.XXX	
X.XXX	X.XXX	
X.XXX - X.XXX	X.XXX - X.XXX	
X.XXX	X.XXX	
	Plitidepsin 2.5mg (N=XXX) xxx (xx.x) xxx (xx.x) xx.x (xx.x, xx.x) xx.x (xx.x, xx.x) xx.x (xx.x, xx.x) xx.x (xx.x, xx.x) xx.x (xx.x) xx.x (xx.x) x.xxx x.xxx x.xxx x.xxx x.xxx x.xxx	Plitidepsin 2.5mg (N=XXX)         Plitidepsin 1.5mg (N=XXX)           XXX (XX.X)         XXX (XX.X)           XXX (XX.X)         XXX (XX.X)           XXX (XX.X)         XXX (XX.X, XX.X)           XX.X (XX.X, XX.X)         XX.X (XX.X, XX.X)           XX.X (XX.X)         XX.X (XX.X, XX.X)           X.XXX         X.XXX           X.XXX         X.XXX

N = number of patients in analysis set. % = percentages are calculated based on N as the denominator.

CI = Confidence interval; SE = Standard Error.

Notes: Sustained (ie, with no subsequent readmission to Day 31) hospital discharge (in days), defined as the first day, from randomisation through completion of the study, on which a patient

i. discharges from the hospital, and

ii. has no subsequent re-admission

[a] Calculated using the Kaplan-Meier estimator. CIs derived based on Brookmeyer-Crowley method and using a log log transformation.

[b] 2-sided p-values calculated using a stratified log-rank test, including the fixed effect of the treatment group and levels of the randomisation stratification factors, ie, geographical region (Europe vs. Rest of the World), Charlson Comorbidity Index (0-1 vs. >1) and pre-baseline Barthel index ( $\geq$ 90 versus <90) as derived using the eCRF data as covariates.

[c] Stratified log-rank test p-values adjusted for multiplicity using the Hochberg step-up procedure.

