# 5. FIGURES

#### Figure 14.2.1.1 Time to Sustained Withdrawal of Oxygen Supplementation - Kaplan-Meier Plot (Intent-To-Treat Population)

Notes: Sustained withdrawal of oxygen supplementation (in days) with no subsequent reutilisation during remaining study period is defined as the first day, from randomisation through completion of the study, on which a patient

i. satisfies categories 0 to 4 on the 11-point WHO Clinical Progression Scale, and

ii. has no subsequent reutilisation of oxygen supplementation (5 to 10 on the 11-point WHO Clinical Progression Scale)

Reference: Table 14.2.1.1.1

Type of figure	Kaplan-Meier Plot
Figure Template ID	FG002
Treatment display details	For line and symbols, follow Section 2.12 Graphical Presentations
X-axis label	Time to Sustained Withdrawal of Oxygen Supplementation (days)
X-axis Scale	Major tick - 0-42 by 3, Minor tick - Nil
Y-axis label	Cumulative Proportion of Sustained Withdrawal of Oxygen Supplementation (1-Cumulative Survival)
Y-axis Scale	0.0 to 1.0 by 0.1
Legend	Line patterns for Plitidepsin 2.5mg, Plitidepsin 1.5mg, Control Arm
Legend position	Appear inside plot, bottom right
Annotations	Display 'Numbers of patients at risk' at the start of the corresponding day on the x-axis
	Display censoring symbol legend inside plot, top left
Other notes	Parameter option for symbol statement: Interpol = step

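### Oxygen-withdrawal and discharge events count to study completion, but remaining non-events are censored at the Day 31 visit, so any later event distorts the Kaplan-Meier tail

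*SAP*

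**What the plan says.** The note to Table 14.2.1.1.1, like section 7.6.1, says that sustained oxygen withdrawal "is defined as the first day, from randomisation through completion of the study, on which a patient" satisfies the two criteria. Section 7.6.1 then treats patients without the event in two steps. First, "in case of early study discontinuation due to any reason the patient will be censored at the date of the early study discontinuation". Then: "Otherwise, the patient will be censored at the date of the Day 31 visit or death date, whichever is first".

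The key secondary endpoint follows the same pattern. Section 7.6.2.1 has it "defined as the first day, from randomisation through completion of the study, on which a patient" is discharged without readmission, and Table 14.2.2.1.1 repeats this: "hospital discharge (in days), defined as the first day, from randomisation through completion of the study". For patients without that event who do not leave the study early, "the patient will be censored at the date of the Day 31 visit or death date, whichever is first".

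Section 2.2 does not end a patient's participation at the Day 31 visit. It runs to that visit or "until resolution/ stabilisation of treatment-related AEs, TEAEs of special interest, and SAEs that occurred through Day 31, whichever is longer".

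**The concern.** The event window is open and the censoring window is closed. Take two patients still on oxygen in hospital at Day 31, each with an unresolved SAE. The one who comes off oxygen on Day 38 is an event at Day 38. The one who never does is censored at the Day 31 visit. Whether a patient is at risk after that visit thus depends on what later happens to that patient, which the Kaplan-Meier estimator does not allow.

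Such late dates could be in the data. Appendix 4, footnote 13, has clinical status scored daily in hospital and gives no end date for this. Listing 16.2.6.3 dates each change of hospital status.

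At stake are the tail of the primary and key secondary curves, the Kaplan-Meier mean and SE that 7.6.1 and 7.6.2.1 require without a truncation time, the event n (%), and any percentile not reached by Day 31. Event status also decides which patients enter the addendum tables that split the population by whether sustained withdrawal was achieved, for example Tables 14.1.2.1.2 and 14.1.2.1.3.

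**Working it through.** **Plan's own figures.** Section 2.3 gives HR 1.4, one-sided alpha 0.0125, 80% power, a rho = 1.18 futility look at 116 events per pair, 353 events per pair and 530 events in 609 patients.
- Schoenfeld: 4 × (2.2414 + 0.8416)² / (ln 1.4)² = 4 × 9.505 / 0.1132 = 336 events without the futility look.
- With the futility look, power at 353 events is 80.0%, and 353 × 1.5 = 529.5, so 530. The design reproduces.
- Planned event share: 530 / 609 = 87.0%. The first illustration is built to match it.

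**Illustrative arm (event times are assumptions).** 203 patients with 177 events by Day 30 (177 / 203 = 87.2%). Day 31 visits are spread over Days 28 to 34, as the ±3-day window allows. Study day and days since randomisation are treated as the same.
- No late event: 1−KM ends at 87.4%, so S = 0.126. This is slightly above 87.2% because some patients are censored before the last event.
- One event at Day 38: every other patient has left the risk set, so n = 1 and S = 0.126 × (1 − 1/1) = 0. 1−KM is 100%, against a crude share of 178 / 203 = 87.7%.
- KM mean, taken to the last event time: 12.3 + 0.126 × (38 − 30) = 13.3 days.
- One event at Day 33 with 10 at risk: 1 − 0.126 × 9/10 = 88.6%.
- One event at Day 34 with 5 at risk: 1 − 0.126 × 4/5 = 89.9%.
- The 75th percentile is Day 18 throughout.

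**Fewer early events.** With 150 of 203 events by Day 30 (73.9%), the 75th percentile is not reached. One Day 38 event makes it 38 days, takes 1−KM to 100%, and moves the KM mean from 13.7 to 13.7 + 0.261 × (38 − 28) = 16.3 days.

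**Same data with one horizon.** With events and censoring both closed at Day 31, 1−KM ends at 87.4% in the first case and 73.9% in the second. In the second case the 75th percentile stays not reached.

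**Log-rank test.** Two arms of 203, with 184 and 170 events by Day 30, give Z = 3.093. One late control event with one patient at risk across both arms contributes O − E = 1 − 1 = 0 and variance 0, so Z stays at 3.093. Four late control events plus two late plitidepsin events give Z = 3.155.

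**The case against.** The strongest reply is that completion was meant to be the Day 31 visit. Appendix 4, footnote 23, labels Day 31 the end-of-study visit for safety and efficacy, and the schedule has no later column. The lost-to-follow-up rule in 7.6.1, the restricted-mean times in 7.6.3 and the periods in Table 1.1 all stop at Day 31. The extension in section 2.2 is about resolving adverse events, not scoring efficacy. This is a plausible account of the intention, and late events may be few or absent. But section 2.2 states a different end of study, and nothing in the SAP truncates events at Day 31. Two programmers could therefore derive different event counts.

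Several stronger readings are tempting but not supported:
- A reader might infer that every non-event is cut at Day 31. Deaths and early discontinuations are censored at their own dates.
- The effect does not start sharply at Day 31. Inside the visit window other patients are still at risk, and the jump is small.
- The sustained test for discharge is not open-ended. The endpoint definition already limits the readmission check to Day 31, although criterion ii does not repeat the limit. It does not limit the discharge date.
- The plot axis ("Major tick - 0-42 by 3, Minor tick - Nil") does not show that late events were expected. It is the setting on all the Kaplan-Meier figures, including mortality.
- Late follow-up tied to adverse events could differ between arms, but the SAP gives no figures showing that it does.

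**Conclusion.** The concern holds as a mismatch in the written rules for both endpoints. Read literally, one event after the last Day 31 visit is enough to send an arm's curve to 100% whatever its level before. The KM mean moves by about 1 day in the first illustration and 2.6 days in the second, and a 75th percentile not reached by Day 31 can acquire a value.

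This is not a threat to the primary test. A reader might infer a biased p-value or hazard ratio. The log-rank check does not support that, and percentiles reached by Day 31 do not move.

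The conclusion requires at least one recorded withdrawal or discharge after the last Day 31 visit. The event counts and late dates used here are illustrative. The SAP does not say how many such events there are, so no frequency for the problem can be given.

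**What to change.** Use one horizon. In 7.6.1 and 7.6.2.1, count events only through the Day 31 visit and judge oxygen reutilisation to that same date. Repeat the existing Day 31 limit on readmission inside criterion ii. Censor patients without a sustained event by then at that visit, or at earlier discontinuation or death. List later events separately.

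Carry the wording into every place that repeats the definitions:
- the extended definition in 7.6.1 and the Table 14.2.1.x and 14.2.2.x notes;
- Tables 14.2.3.22, 14.2.4.1, 14.2.4.2, 14.2.4.3.1 and 14.2.4.3.2;
- Figures 14.2.1.1, 14.2.1.2, 14.2.2.1, 14.2.2.2 and 14.2.2.8;
- in the addendum, Tables 14.2.4.1.1, 14.2.4.1.2 and 14.2.4.2.1 and Figure 14.2.1.2.1.

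Time to immune-modulating drugs and time to antiviral drugs (7.6.2.3) have the same open event window and closed censoring, and should be aligned.

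The cost is wording plus one line in the derivation. The downside is that a few late recoveries no longer count as events. Comparing the event dates in Listings 16.2.6.5 and 16.2.6.6 with each patient's Day 31 visit date would show whether any result changes.
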